5. STUDY PROCEDURES AND RANDOMISATION

Prior to patient recruitment, the machine learning algorithm will be run centrally at NHS Hounslow Clinical Commissioning Group, Hounslow House. It will be run across 46 general practice databases in the Hounslow area, which includes an estimated population of 315 000 people.

The algorithm will generate an anonymised list of high- risk AF individuals with their associated general practice. It is expected that this will be approximately 9 000 people.

Each general practice will be clustered into three different sets depending on the size of the population of high- risk AF patients found at that practice. The sets are classed into large (>200 patients identified screen), medium (100-200 patients) and small (< 100 patients). This will allow the GP practices to be later cluster randomised into four groups corresponding to the different screening strategies, with roughly equal number of large/medium/small GP practices in each group. These four groups that we will compare are: (1) ECG group, (2) holter monitoring group, (3) a PPG monitoring group and (4) a long term AliveCor monitoring group.

5.1 RECRUITMENT

Following this, each general practice will be visited separately and the algorithm will be run at each individual practice to identify individual high-risk AF patients. A member of each general practice will be shown how to run the algorithm and will run it on the database of the general practice. High-risk AF participants will be invited to be recruited into the study by a member of the general practice team. Every effort will be made to recruit vulnerable adults who lack capacity so they can be recruited if they wish to be involved. All high -risk participants recruited will be registered and flagged up on a depersonalised health data set covering the North West London (NWL) population, known as the Discover dataset, which is the NWL health research cohort register. This will allow the retrieval of health care data of these participants while keeping their anonymity. Each participant will have an anonymous identifier number. Approval for this has been sought from NWL Data Access Committee.

6. ADVERSE EVENTS

6.1 DEFINITIONS

Adverse Event (AE): any untoward medical occurrence in a patient or clinical study subject.

Serious Adverse Event (SAE): any untoward and unexpected medical occurrence or effect that:

- Results in death
- **Is life-threatening** refers to an event in which the subject was at risk of death at the time of the event; it does not refer to an event which hypothetically might have caused death if it were more severe
- Requires hospitalisation, or prolongation of existing inpatients' hospitalisation
- Results in persistent or significant disability or incapacity
- Is a congenital anomaly or birth defect

Medical judgement should be exercised in deciding whether an AE is serious in other situations. Important AEs that are not immediately life-threatening or do not result in death or hospitalisation but may jeopardise the subject or may require intervention to prevent one of the other outcomes listed in the definition above, should also be considered serious.

6.2 REPORTING PROCEDURES

All serious & non serious adverse effects, whether expected or not, will be recorded. Depending on the nature of the event the reporting procedures below will be followed. Any questions concerning adverse event reporting will be directed to the Chief Investigator in the first instance.

Non serious AEs

All such events, whether expected or not, will be recorded.

Serious AEs

An SAE form will be completed and faxed to the Chief Investigator within 24 hours. However, relapse and death due to any pre-existing medical or surgical conditions and hospitalisations for elective treatment of a pre-existing conditions will not be reported as SAEs.

All SAEs will be reported to the London- Bloomsbury REC where in the opinion of the Chief Investigator, the event was:

- 'related', ie resulted from the administration of any of the research procedures; and
- 'unexpected', ie an event that is not listed in the protocol as an expected occurrence

The Chief Investigator will inform the sponsor of the study of all SAEs. Reports of related and unexpected SAEs will be submitted within 15 days of the Chief Investigator becoming aware of the event.

Local investigators will report any SAEs as required by their Local Research Ethics Committee and/or Research & Development Office.

Contact details for reporting SAEs CI email ([name]; [contact])

7. SCREENING AND FOLLOWUP

Participants' care will continue under their normal clinical or healthcare teams. Therefore, their followup will be arranged by and conducted by these team(s).

Following recruitment into the study, each participant will be invited for screening for AF at their practice or a research clinic at West Middlesex University Hospital.

At the baseline assessment, each participant will be required to have a single lead ECG recording for a minimum of 30 seconds using an AliveCor device (two metal pads on a plastic strip, Figure 2) and smartphone which will be provided by the research team. Figure 3 demonstrates the use of the device with a smartphone. For a recording, at least 1 finger is required to rest on each of the metal pad (electrodes). If AF is identified from this recording, the patient will be referred back to their practice for appropriate treatment.

Figure 2: AliveCor device

[figure not shown]

Figure 3: AliveCor recording

Participants without a diagnosis of AF in the holter monitoring group, photoplethysmography (PPG) monitoring group and the long term AliveCor monitoring group will be given a health technology to take away. They will have monitored with this technology for 3 months. The technology that they receive will be based on the monitoring group they belong to. The ECG group will not have any further monitoring.

For the holter monitoring group, the participants will receive a 72-hr holter monitor/ECG patch initially, and two further 24-hr holter monitors/ ECG patches at 6 and 12 weeks. These will be returned to the research team following completion of each monitoring period.

For the Photoplethysmography (PPG) monitoring group, the participants will be given access to a smartphone application called Fibricheck to use on their own smartphone. The participant will be provided with a QR code to scan for the prescription of 3- month

monitoring period. The participant will need to download the Fibricheck App on their own smartphone from the App store. They will then need to scan the QR code with the Fibricheck App. The participant will then be able to start making recordings by placing their finger on the camera for 1 minute. Figure 4 demonstrates how to set the Fibricheck App on a smartphone and Figure 5 shows how to take a recording with the App.

[figure not shown]

Figure 4: How to set up Fibricheck App on smartphone

[figure not shown]

Figure 5: How to take a recording using the Fibricheck App

The participants will be asked to perform twice daily recordings lasting 1 minute each using the camera light of their smartphone. If they have symptoms, they can also make further recordings. They will also be able to annotate the recording afterwards with their symptoms. The recordings will be performed over a period of 3 months. Following each recording, feedback will be given. The recordings will be sent to Fibricheck's secure cloud. Irregular results will be reviewed by Fibricheck's monitoring center under the supervision of cardiologists. The clinical research team will have access to all participant's data via the physician dashboard. They will regularly review the data on a weekly basis and will inform the participant if irregular results are seen which warrant further management. The clinical research team will also receive daily emails including notifications of any participants with new heart rhythm disturbances.

If a recording alerts an irregular pulse notification, the participant will be invited to their practice or a research clinic at the West Middlesex University Hospital to have a single lead ECG with AliveCor device or 12-lead ECG or a Holter monitor to detect AF.

For the long term AliveCor monitoring group, the participants will be given access to a smartphone application called Kardia to use on their own smartphone. They will also be a metal pad AliveCor device. The procedure for taking a recording will be explained when given access to the application and device. They will be asked to make twice daily recordings using the application and submit it to the research team for 3 months.

If AF is identified at any point during the 3- month monitoring period, the patient will be referred back to their practice for appropriate treatment.

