3. STUDY DESIGN

This will be a 1.5-year study in which participants will be recruited prospectively from databases of 46 general practices (GPs) in the Hounslow area. Our machine learning algorithm will be used on these databases to identify our participants. Our participants will be identified as those at risk of developing atrial fibrillation. The practices will be cluster randomised into 4 groups. The high- risk AF individuals will be invited for screening for AMLA-AF protocol, version 1.1 25/10/21, IRAS Project ID: 293493

AF. The four groups are as follows: (1) ECG group (2) Holter monitoring group, (3) a Photoplethysmography (PPG) monitoring group and (4) a long term AliveCor monitoring group.

All individuals who have agreed to participate in the study will be screened initially once with a single lead ECG recording using an AliveCor device. This will be done either at their general practice or a research clinic at West Middlesex University Hospital. Any individual found to have AF will be followed up by their general practice to receive appropriate treatment. They will also not be required to have any further screening.

After this initial screening, if an individual has not been found to have AF and belongs to groups 2-4, they will undergo further screening for a period of 3 months. This will be based on their allocated group. They will be able to take their screening technology home. Again, if any individual is found to have AF, they will be followed up by their general practice to receive appropriate treatment.

Participation in this study will be entirely voluntary and will not affect participants' current or future care. Participants will be free to withdraw from the study at any time without having to provide a reason. Participants will be recruited prospectively from general practices, on a first-come first-serve basis, to minimise bias. Recruitment will continue throughout the study.

Data collected from participants prior to drop out or loss to follow-up will be included in the data analysis. We are not aware of any ongoing studies that are competing for the same group of participants or whose results may affect recruitment. Similarly, our study will not jeopardise other studies either.

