3.1 STUDY OUTCOME MEASURES

The primary endpoint will be the detection of atrial fibrillation with a one-off ECG. The diagnostic yield of the machine learning algorithm will be analysed.

The diagnostic yield for AF detection of each health technology will be analysed. The time to first detection of AF will also be measured for each health technology.

Selective analysis will be performed looking at diagnostic yield for AF detection for different rhythm monitoring strategies which vary in frequency and duration.

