8. STATISTICS AND DATA ANALYSIS

It is estimated that 9 000 participants will be identified to be high risk for AF. Taking into account the dropout from previous screening exercises, we estimate that 1 800 (20%) participants will belong to the four groups.

The diagnostic yield for AF detection will be analysed for the machine learning algorithm and each health technology.

There will be selective analysis of the data collected from the monitoring groups to determine the optimal frequency and duration.

For each participant for the holter monitoring group, two rhythm histories will be created. The first rhythm history will just include the results of 72hr monitor. The second rhythm history will include the results of first 24hrs of the 72hr monitor, the results of the second 24hr monitor and the third 24hr monitor. This will allow the screening strategies of 3 x24hr monitoring and 1 x 72hr monitoring to be compared. The diagnostic yield of AF detection for the two strategies will be compared.

The data from the PPG and long term AliveCor monitoring groups will then be selectively analysed with some recordings blanked from analysis to compare the diagnostic yield of different durations (1-month vs 3 months) and different frequencies (Daily vs alternate days vs weekly).

Data analysis will be performed at West Middlesex University Hospital.

All high-risk AF patients will be followed up for the detection of AF. This will be at least 1 year from the last recruited patient.

The end of the study will be defined as last followup required for the purposes of the study.

Data and all appropriate documentation will be stored for a minimum of 10 years after the completion of the study, including the follow-up period.

AMLA-AF protocol, version 1.1 25/10/21, IRAS Project ID: 293493

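### Contrasts with the ECG group set three months of device detection against a count that closes at day 0, and no stated outcome brings the planned AF follow-up into the four-group comparison

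*Protocol*

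**What the plan says.** Protocol section 5 randomises practices and names the arms of the comparison: "These four groups that we will compare are: (1) ECG group, (2) holter monitoring group", then the PPG and long-term AliveCor groups. Under section 3 every participant has the same single-lead baseline recording. A participant who is negative on it and "belongs to groups 2-4, they will undergo further screening for a period of 3 months". For the remaining group, section 7 states: "The ECG group will not have any further monitoring".

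The outcomes are in section 3.1:
- Primary: "The primary endpoint will be the detection of atrial fibrillation with a one-off ECG".
- Yield by technology: "The diagnostic yield for AF detection of each health technology will be analysed". Time to first detection is likewise measured for each technology.
- Selective analyses of monitoring frequency and duration.

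Two further statements matter. Section 8 says "All high-risk AF patients will be followed up for the detection of AF" and, of the length, "This will be at least 1 year from the last recruited patient". Section 5.1 says that "participants recruited will be registered and flagged up on a depersonalised health data set" (the Discover dataset), so that their health care data can be retrieved.

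**The concern.** The ECG group is a randomised group that receives the one-off recording and nothing more. Its main value in a group comparison is to show how much AF comes to light in ordinary care while the other groups are being monitored. The outcomes in section 3.1 do not use it that way. Because yield is attributed to a technology, and this group's technology is used once, its count is final at day 0. A monitored group has the same recording plus three months of further chances, so its expected cumulative yield cannot be lower.

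At stake is the interpretation of the gain. A technology would be credited with every case it picks up, including cases the practice would have diagnosed in the same window. The figure a commissioner needs, namely what three months of monitoring adds to a single ECG under usual care, is the net one.

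**Working it through.** **1. Each stated outcome, read for the ECG group**

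- One-off ECG (primary): the same test in all four groups, taken before their monitoring differs. It is sound as a measure of the algorithm's yield, but it does not contrast monitoring strategies.
- Yield of each technology: the ECG group's count closes at day 0, while groups 2 to 4 go on counting for three months.
- Time to first detection by technology: in the ECG group, day 0 or never.
- Frequency and duration (sections 3.1 and 8): Holter, PPG and long-term AliveCor data only.
- AF follow-up (section 8): covers the ECG group too, but is not linked to allocated group or to a section 3.1 outcome. Its length is set from the last recruit, so it gives no common per-participant window.

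Only the last item can inform a fair contrast with the ECG group, and it is the one not attached to the comparison.

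**2. The plan's own figure**

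Section 8 expects 20% of 9,000 to take part: 0.20 × 9,000 = 1,800, which reproduces. The protocol gives no significance level, power, effect size, three-month yield or usual-care rate, so there is nothing further to reproduce.

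**3. Illustration of gross against net**

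Inputs:
- Group size: 1,800 / 4 = 450 (equal split assumed).
- AF at baseline: 450 / 9 = 50, leaving 400. This takes the number needed to screen of 9 in section 1 as the yield of one baseline recording, which section 1 does not say.
- Gross three-month yield g: 2%, 4% or 6% (assumed).
- Usual-care AF over the same three months u: 0.25% to 1.5% (assumed), that is 1 to 6 cases per 400.

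Formulae: net gain = g − u; share of the gross yield that usual care would also have found = u / g. Both take every usual-care case to be one the device would also detect, so for each pair u / g is an upper limit.

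| g (cases per 400) | Net, u = 0.25% | Share | Net, u = 1.5% | Share |
|---|---|---|---|---|
| 2% (8) | 1.75% | 12.5% | 0.5% | 75% |
| 4% (16) | 3.75% | 6.25% | 2.5% | 37.5% |
| 6% (24) | 5.75% | 4.2% | 4.5% | 25% |

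A second set of assumptions gives a similar spread. Usual-care rates of 2% to 8% per year convert by 1 − exp(−rate × 0.25) to 0.50% to 1.98% in three months. Against gross yields of 3% to 6%, the share runs from 0.50 / 6 = 8% to 1.98 / 3 = 66%. In both sets the extremes come from pairing the lowest value of one input with the highest of the other.

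**4. Effect on precision**

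At g = 4% with 400 per group, two-sided 5% and clustering ignored, power is 98% against a fixed zero. Against a counted usual-care rate it is 96% at u = 0.25% and 58% at u = 1.5%. Clustering by practice would be expected to lower these figures.

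**The case against.** The strongest reply is that the protocol does follow the ECG group. Section 8 promises AF follow-up of all high-risk patients, which spans the three-month window, and section 5.1 gives the data route. A reader might infer from sections 3.1 and 7 that usual-care AF in the ECG group goes uncollected, that the trial therefore cannot show what monitoring adds, or that the ECG practices contribute nothing beyond a test everyone has. The documents do not support any of these. The data are to be collected, the ECG group contributes fully to the primary endpoint, and its follow-up is the unmonitored comparator that is needed.

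It can also be said that the study summary lists AF detection as an outcome without restricting it to study devices, that windows and reference groups are commonly left to an analysis plan not shown here, and that a technology's yield properly means what it detects. Earlier detection is itself a stated aim (section 1).

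Much of this stands. Device yield is a legitimate descriptive figure, and the choice of statistical model can wait for the analysis plan. But section 3.1 is not silent on which event counts: it attributes yield and time to detection to each technology. That definition cannot give a fair contrast with the ECG group, which section 5 says will be compared. Earlier detection is a benefit, but it differs from additional detection, and gross yield does not separate the two.

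**Conclusion.** The point holds in a limited form. On the outcomes as stated, any contrast of a monitored group with the ECG group sets three months of device detection against a count closed at day 0, so the apparent gain is gross of usual-care detection. The protocol plans to collect the AF needed to correct this, but does not bring it into the four-group comparison or set a common window for it.

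The reach is confined to contrasts with the ECG group. The primary endpoint is measured identically in all groups, groups 2 to 4 share the same monitoring window, and the frequency and duration analyses are made within groups.

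The size is unknown. The illustrative 4% to 75% rests wholly on assumed monitored yields and usual-care rates, on an equal split and on complete overlap of usual-care and device-detected cases. It shows only that the gap could be small or large.

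**What to change.** In sections 3.1 and 8, define the outcome for the four-group comparison as first AF diagnosis from any source (study recording or routine record) within three months of the baseline ECG, among those AF-free at baseline, by allocated group. Name the ECG group as reference and report each monitored group minus the ECG group as the net gain. State that the follow-up already planned in section 8 supplies the routine-record diagnoses. Keep device-detected yield and time to detection as separate, technology-specific results.

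The cost is wording plus one record extract at three months for participants already registered on the Discover dataset, carrying allocated group and baseline date. No extra visits, tests or participants are needed. The downsides are that routine records capture AF passively, and that the net gain will be smaller and less precise than the gross yield.

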8. STATISTICS AND DATA ANALYSIS

It is estimated that 9 000 participants will be identified to be high risk for AF. Taking into account the dropout from previous screening exercises, we estimate that 1 800 (20%) participants will belong to the four groups.

The diagnostic yield for AF detection will be analysed for the machine learning algorithm and each health technology.

There will be selective analysis of the data collected from the monitoring groups to determine the optimal frequency and duration.

For each participant for the holter monitoring group, two rhythm histories will be created. The first rhythm history will just include the results of 72hr monitor. The second rhythm history will include the results of first 24hrs of the 72hr monitor, the results of the second 24hr monitor and the third 24hr monitor. This will allow the screening strategies of 3 x24hr monitoring and 1 x 72hr monitoring to be compared. The diagnostic yield of AF detection for the two strategies will be compared.

The data from the PPG and long term AliveCor monitoring groups will then be selectively analysed with some recordings blanked from analysis to compare the diagnostic yield of different durations (1-month vs 3 months) and different frequencies (Daily vs alternate days vs weekly).

Data analysis will be performed at West Middlesex University Hospital.

All high-risk AF patients will be followed up for the detection of AF. This will be at least 1 year from the last recruited patient.

The end of the study will be defined as last followup required for the purposes of the study.

Data and all appropriate documentation will be stored for a minimum of 10 years after the completion of the study, including the follow-up period.

AMLA-AF protocol, version 1.1 25/10/21, IRAS Project ID: 293493

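### The Aim 3 strategy comparisons reuse one record per participant that AF detection can cut short, and the protocol does not say whether recording continues or how absent recordings count

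*Protocol*

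**What the plan says.** Aim 3 (section 2) is to find the best duration and frequency of rhythm monitoring. Section 8 gives the method.

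- **Holter group.** Every participant gets two rhythm histories. The first is the 72-hour monitor alone. For the other, "The second rhythm history will include the results of first 24hrs of the 72hr monitor", to which the two later 24-hour monitors are added. The yields of the two histories are compared. Section 7 places the later monitors at 6 and 12 weeks and has each device returned after its own period, so the 72-hour result can be known before week 6.
- **PPG and long-term AliveCor groups.** The data are "selectively analysed with some recordings blanked from analysis to compare the diagnostic yield of different durations" (1 versus 3 months) and frequencies (daily, alternate days, weekly).

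On what follows a detection:

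- After AF at the initial ECG, section 3 is explicit: "They will also not be required to have any further screening".
- For AF found later, section 3 says "Again, if any individual is found to have AF, they will be followed up by their general practice to receive appropriate treatment", and section 7 says "If AF is identified at any point during the 3- month monitoring period, the patient will be referred back to their practice for appropriate treatment". Neither says whether the remaining recordings are made.

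Section 3 keeps data collected before drop-out. No section says how a participant is classified when later recordings are absent because AF had already been found.

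**The concern.** Comparing strategies within one person's record is efficient, but it needs the record to contain the recordings that each strategy would have used. Here the record is collected under a process that acts on AF as soon as it is seen.

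Take a Holter participant whose AF appears only in hours 25 to 72. The 72 h history is positive. The 3 x 24 h history depends on the week-6 and week-12 monitors. If those are not worn because AF is already known, this history has no chance to become positive. The same applies to a smartphone participant whose first AF recording falls on a blanked day: any later retained recording that could have shown AF may never be made.

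If such histories are read as showing no AF, the yield of 3 x 24 h and of the less frequent schedules is biased downward. Part of the difference between strategies would then come from how the record ended. Aim 3 rests on these comparisons. If recordings stop, no later analysis document can recover them.

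**Working it through.** **The plan's own figure.** "It is estimated that 9 000 participants will be identified to be high risk for AF" and "we estimate that 1 800 (20%) participants will belong to the four groups": 9 000 x 0.20 = 1 800, which reproduces. An equal split (assumed) gives 1 800 / 4 = 450 per group. The protocol states no yield, error rate or power for Aim 3, so there is no further figure to reproduce.

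**Assumptions.** All detection probabilities, correlations and lags below are assumed; the protocol gives none. Recording is taken to stop at detection, and absent recordings to add no detection. Yields are among participants with paroxysmal AF.

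**Holter, independent days.** Let p be the probability that a 24-hour period shows AF.

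- 72 h yield = 3 x 24 h yield on complete data = 1 - (1-p)^3
- Apparent 3 x 24 h yield = p + (1-p)^3 [1 - (1-p)^2]: AF in the first 24 h, or none in 72 h and then AF on a later monitor
- Left undetermined = (1-p)[1 - (1-p)^2]: AF first seen in hours 25 to 72
- Upper bound (all of these counted as detected) = apparent + undetermined

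| p | Complete data | Apparent (lower bound) | Undetermined | Upper bound |
|---|---|---|---|---|
| 0.05 | 14.3% | 0.05 + 0.857 x 0.0975 = 13.4% | 0.95 x 0.0975 = 9.3% | 22.6% |
| 0.10 | 27.1% | 0.10 + 0.729 x 0.19 = 23.9% | 0.90 x 0.19 = 17.1% | 41.0% |
| 0.20 | 48.8% | 0.20 + 0.512 x 0.36 = 38.4% | 0.80 x 0.36 = 28.8% | 67.2% |

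The two strategies are equal by construction, yet 3 x 24 h appears worse by 0.9, 3.2 and 10.4 points.

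**Holter, correlated adjacent days.** With correlation r between adjacent days and the later monitors independent, P(no AF in 72 h) = (1-p)[1 - p(1-r)]^2.

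- p = 0.20, r = 0.3: 0.8 x 0.86^2 = 0.592. 72 h 40.8%; 3 x 24 h complete 48.8%; apparent 0.20 + 0.592 x 0.36 = 41.3%. The advantage of +8.0 points shrinks to +0.5.
- p = 0.10, r = 0.6: 0.9 x 0.96^2 = 0.829. 72 h 17.1%; complete 27.1%; apparent 0.10 + 0.829 x 0.19 = 25.8%. The advantage of +10.0 points shrinks to +8.7.
- p = 0.30, r = 0.3: 0.7 x 0.79^2 = 0.437. 72 h 56.3%; complete 65.7%; apparent 0.30 + 0.437 x 0.51 = 52.3%. The advantage of +9.4 points becomes -4.0.

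The true advantage is always reduced. Whether the ranking changes depends on inputs that nobody has yet.

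**Smartphone groups.** Simulation over 90 days, with per-day detection q, whole days retained starting with the first, and recording stopped at the first positive day:

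| q | Alternate-day: complete vs apparent | Weekly: complete vs apparent |
|---|---|---|
| 0.01 | 36.6% vs 29.9% | 12.2% vs 8.7% |
| 0.03 | 74.3% vs 47.3% | 32.6% vs 14.6% |
| 0.10 | 99.1% vs 52.6% | 74.5% vs 19.2% |

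If recording runs on for 7 days after the first positive, the loss is smaller: at q = 0.10, alternate-day 99.1% vs 68.8%.

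**Where there is no bias.** One month is the first part of three months, so its yield needs no recording made after a detection. Continuous AF is seen on the first day, which both Holter histories contain, as does any blanked schedule that keeps that day.

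**The case against.** **Stopping is not stated.** Only AF at the initial ECG explicitly ends screening. In section 3 the word that links later detection to it attaches to practice follow-up. Section 7 schedules the later Holters without condition, section 8 builds both histories for every participant, and section 9.2 lets participants given alternative treatment or monitoring stay in for data collection and analysis. This stands: stopping is a plausible reading, not text. But nothing requires the remaining recordings either, so the record may be incomplete in just those participants who decide the comparison.

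**Negative scoring is not stated.** A reader might infer that the plan counts these participants as missed. No section says so, and an analysis plan that is not shown may treat them as censored. This too stands. What the protocol does fix is a pair of histories for everyone, built from results, with no provision for results that detection itself prevented.

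**Stronger readings that the documents do not support.**

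- That 72 h will win by construction. With correlated days 3 x 24 h can stay ahead.
- That 3 x 24 h is the sparser schedule. Total recording time is equal; only the spacing differs.
- That the bias arises whatever the AF burden. It is small at low burden and nil for continuous AF when the first day is kept.
- That drop-out is the same defect. Failure to complete repeat monitors may be a real property of that strategy.
- That treatment spoils later recordings. The only treatment the protocol names is anticoagulation to prevent stroke (section 1).

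**The numbers of people may be small.** Section 1 mentions one AF case per 9 screened. With 450 per group, 450 / 9 = 50 people with AF. The Holter shortfall is then 50 x 0.032 = 1.6 people at p = 0.10 and 50 x 0.104 = 5.2 at p = 0.20. This is fair, although with so few cases even a small shift matters to a paired comparison.

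**PPG confirmation takes time.** An irregular reading leads to a further ECG or Holter, so recording may go on for a while. This reduces the bias without removing it.

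**Conclusion.** The point holds as a conditional one. If recordings stop once AF is found during monitoring, and absent recordings add no detection, the yields of 3 x 24 h Holter and of the alternate-day and weekly schedules are biased downward. The protocol neither rules out the first condition nor provides against the second.

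The direction follows from how section 8 builds the strategies. The size is illustrative: roughly 1 to 10 points for 3 x 24 h at per-day detection of 0.05 to 0.20, and more for the blanked schedules if recording stops at once. A true 3 x 24 h advantage is reduced and not necessarily reversed. The 1- versus 3-month comparison is unaffected, and so is the primary endpoint, detection on a one-off ECG.

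Severity is moderate, since a secondary aim is touched. It is a cheap improvement.

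**What to change.** 1. State in sections 7 and 8 whether recordings already scheduled continue for data collection after AF is found during monitoring, and reconcile sections 3, 7 and 8 on this. Referral and care stay with the practice; whether monitoring should continue clinically is not a matter for this review.
2. In section 8, where later recordings are absent because AF had already been found, treat them as unobserved, not negative, for the alternative strategy. Report the paired yield comparison with bounds: all such participants detected, and none detected.
3. For the blanked schedules, average over the possible retained-day offsets, so that the result does not hang on which day is kept first. This does not replace item 2: with immediate stopping, each first positive day is retained under one offset in two (alternate days) or one in seven (weekly), so the averaged apparent yield is exactly 1/2 or 1/7 of the daily yield.

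The cost is a few sentences of wording and slightly more analysis, with no new device or visit type. The downside is wider intervals. At p = 0.10 the Holter bounds run from 23.9% to 41.0%, so if recordings do stop, the comparison may be inconclusive, and the report should say so.
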